5. * Describe any potential for direct benefits to participants in this study:

Participants are unlikely to benefit from this study as it is intended for feasibility and acceptability assessment only. However, some participants may experience prevention or reduction in their delirium which would be beneficial to their overall health and potentially decrease some of their healthcare needs.

6. * Describe any potential for direct social impact in this study . For example, any engagement with specific communities to respond to community-identified needs, or ways the study will strengthen the well-being of the specific communities if applicable:

This study will engage participants from both the VCU Health downtown campus (medical respiratory ICU) and participants at VCU's Community Memorial Hospital (general ICU) in rural, South Hill, Virginia. Participants at CMH are being targeting for enrollment given the rural nature of the hospital's location and difficulty in enrolling rural patients into clinical research.

7. Upload a supporting citation list if applicable:

Study Population

1. * Provide the maximum number of individuals that

- 1. May participate in any study interaction or intervention (Including screening, consenting, and study activities) AND/OR**
- 2. You obtain any data/specimens about (regardless of identifiability)**

2. If this is a multi-Center Project, what is the maximum anticipated number of subjects across all sites?

not applicable

3. * Provide justification for the sample size by explaining how you arrived at the expected number of participants and why this number is adequate for answering the research questions:

Our goal is to generate descriptive data examining the feasibility and acceptability of weighted blankets and the use of technology to recruit and support clinical research in a rural patient population.

Sample size is based on the literature regarding targets for pilot studies examining feasibility and acceptability. Our sample will consist of the following:

50 adult medicine ICU patient participants: 25 at VCU Medical Center (VCUMC) and 25 at VCU's Community Memorial Hospital (CMH).

50 legally authorized representatives (upper limit; one for each patient participant)

100 Nurses (upper limit; two for each patient)

100 Medical Providers (upper limit; two for each patient)

Total Enrolled Participants = 300

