Once informed consent is obtained, medical-grade weighted blankets (equal to approximately 10% of the participants body weight up to 20lbs maximum) will be applied to participants by the bedside nurse for a minimum of 6 continuous hours nightly between 7pm-7am and additional hours as desired by the patient, their LAR, or the patient's clinical care team. Weighted blankets of various weights will be readily available on the nursing unit; the study team will communicate with the bedside nurse regarding what weight blanket will be used for each patient enrolled. Hourly rounding by a study champion will be utilized to document blanket use between the hours of 7pm-7am. Participants will remain enrolled in the study until they are withdrawn (either at participant request, administrative due to an adverse event, or at the request of the clinical team), or they are transferred from an ICU level of care. Data will be collected on: (1) feasibility and acceptability of weighted blankets; (2) feasibility and acceptability of technology to promote rural participation; (3) preliminary descriptive data and trends related to delirium, agitation, ventilator days, length of stay; and (4) participant demographics (see Data Collection Spreadsheet supporting document attached). A REDCap database the incorporates all data points needed to answer study aims will be developed with the assistance from the Wright Center Biostatistical Consulting Laboratory. Data analysis will include descriptive statistics and comparison statistics between VCUMC and CMH. Once the patient's participation ends (withdrawn or transferred from an ICU level of care), the patient (if alert and oriented), the patient's LAR, the patient's nurse, and the patient's physicians and/or advanced practice providers (APPs) will be asked to complete an electronic survey based on their experience with the weighted blanket use. Surveys will only be administered if a patient uses the blanket for at least one night. The survey will be in REDCap; no participant identifiers will be used. The survey will be opened by a member of the study team and brought to the participant on a study dedicated iPad. The study team member will remain in close proximity until the participant indicates they are done. At the time, the study team member will collect the iPad and ensure the survey has been closed. Who the patient's nurse and physicians/APPs are for the day will be determined by the ICU's electronic assignment board and/or care team noted in the EHR via the storyboard.

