ID: MS12_HM20027241

View: SF2 - Active Internet Data Collection

Active Internet Data Collection

1. * Describe the platform/technology chosen for collecting the data and transmitting data securely over the internet. If proposing a non-VCU approved platform, give the rationale for selecting the technology instead of a VCU-approved platform.

REDCap (a secure, VCU approved platform) will be used to provide surveys to the healthcare providers, patient participants, and legally authorized representatives (LARs). For the healthcare provider and the LAR, a waiver disclosure will be present at the top of the survey to reinforce the waiver of consent for the survey. A study team member will login, select the correct survey, then give the study specific iPad to the patient, healthcare provider, or LAR as appropriate to complete their respective survey.

2. * Describe how data will be linked or unlinked to identifiers including email addresses, names, and/or IP address.

The data will be unlinked to any identifiers (including email addresses, names, and/or IP address or participant numbers). In order to keep track of the number of surveys completed, the study team will solely be informed of whether or not the survey was completed by each survey contender.

3. * How will you protect your data collection from fraudulent responses:

REDCap is a secure platform, therefore false survey contenders will not have access. A study team member will present the iPad to ensure that only the intending survey contender is able to receive access. The study team member will remain close by, without hovering, to ensure only the intending respondent has access to the survey.

4. * Is there an alternative method for completion of the data collection other than the internet?

Yes

No

5. * Describe how individuals will be able to skip or not answer particular questions. If any questions are mandatory, provide justification.

Individuals have the ability to skip or not answer a question. If there are unanswered survey questions, there will be a warning given before submission. This warning is intended to provide guidance for those that may not be aware that they have an unanswered question. Although a warning is present, individuals will still be able to submit the survey without being mandated to answering a question. None of the survey questions are mandatory.

6. If not including children, describe any procedures used to verify that research participants are adults.

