3. * Is this study conducted by or subject to the approval of State or Local Government and designed to study, evaluate, or otherwise examine public benefit or service programs:

Yes

No

4. * Explain how the research involves no more than minimal risk to the participants (Alternative question phrasing: How do the risk(s) of the research activity for which consent is being waived compare to the risks a person might reasonably experience in normal everyday life?):

LARs and healthcare providers will be asked to complete a survey about their experience with use of weighted blankets. Their decision to not participate in survey completion will have no impact on the care of the patient enrolled in the study. Additionally, completion, or lack thereof, will have no impact on the healthcare providers employment at VCU. There will be no identifiers on the survey - they study team is only interested in the feedback given within the surveys and will only maintain a log of number of surveys completed.

5. * Explain how the research could not practicably be carried out without the waiver or alteration (Alternative question phrasing: Why would obtaining consent from participants make the study not achievable or not viable?):

This study aims to examine the acceptability of use of weighted blankets. Data obtained from LARs and healthcare providers regarding blanket use is therefore critical to the aims of this study. It would be time prohibitive for the study team to obtain informed consent from each LAR and healthcare provider completing a survey. Additionally, the study team would then need to link each survey with a participant ID which is not desired given the complete anonymity being sought.

6. * Explain why this study can only be carried out using identifiable or de-identified information/biospecimens.

- Studies with Department of Justice funding may state "Not applicable." (Alternative question phrasing: Why would it be impossible to conduct the study using only anonymous information/biospecimens?):

There will be no identifiers on the survey - they study team is only interested in the feedback given within the surveys and will only maintain a log of number of surveys completed. They study team desires to provide both LARs and healthcare providers completing the surveys complete anonymity.

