Risk Benefit Complete

- Protocol Progress:
- ? INITIAL SETUP
 - ? BACKGROUND, RATIONALE & GOALS
 - ? RESEARCH PLAN
 - ? CONSENT PLAN
 - ? RISKS, PRIVACY & CONFIDENTIALITY
 - ? POPULATIONS WITH SPECIAL CONSIDERATIONS
 - ? INSTITUTIONAL REQUIREMENTS
 - ? DOCUMENTS

Click Continue below to go to the next section

ID: MS12_HM20027241 View: SF2 - Populations with Special Considerations

Populations with Special Considerations

1. * Check all participant groups that will be either

a) Specifically included in this study or

b) Discernable in the research data/specimens.

(Selections will branch)

- Children
- Emancipated minors
- Wards of the State
- Pregnant women or fetuses
- Neonates or Post-delivery Materials
- Prisoners
- Decisionally Impaired Adults**
- VCU / VCUHS students or trainees
- VCU / VCU Health System employees**
- Individuals with limited English proficiency
- Active military personnel
- Student populations in K-12 educational settings or other learning environments
- Members of a federally recognized American Indian and Alaska Native tribe
- None of the Above

2. Additional considerations for VCU/VCU Health System employees:

* Describe how the study will minimize the possibility of coercion to participate.

VCU nurses, physicians, and APPs ("healthcare providers") will be invited to complete a survey at the end of a patient's participation in the study. The survey does not contain any sensitive information. Healthcare providers will be approached and asked if they are willing to complete a survey using the study iPad. Within the survey, information will clearly state the their willingness to complete the survey is completely voluntary. The survey will in no way be linked to the healthcare provider so there is no record of whether individual providers completed the survey or not.

ID: MS12_HM20027241

View: SF2 - Decisionally Impaired Adults

Decisionally Impaired Adults

1. * Choose the nature of the decisional impairment participants will have:

- Temporarily Incompetent to Give Consent**
- Permanently Incompetent to Give Consent
- Unknown

2. * Explain why this population is necessary for the conduct of the study.

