The study team will emphasize that the completion of the survey is voluntary and will in no way affect care of the patient enrolled in the study. The study team member will remain close by to ensure only the intended recipient receives the survey. However, they will be sure to not hover and allow the healthcare provider as much time as needed to complete the survey.

10. * How much time will participants be given to make a decision:

Once the healthcare provider is provided the survey and they have a chance to read the instructions, they will immediately be asked to complete the survey or return the iPad to the study team member without completing the survey.

11. If applicable, describe the procedures for consenting children upon entering adulthood or participants who are no longer decisionally impaired:

ID: MS12_HM20027241

View: SF_IRB_ConsentPlan_Groups

Consent Groups

1. * Enter a descriptive name for this consent / assent group:

Legally Authorized Representative (LAR)

2. * Select all that apply to this consent / assent group:

- | Name |
|---|
|  Signed Consent by Participant |
|  Signed Parent/Guardian Permission or Legally Authorized Representative Consent |
|  Signed Assent by Child or Decisionally Impaired Adult |
|  Verbal/Other Indication of Assent by Child or Decisionally Impaired Adult |
|  Short Form Consent (limited applicability) |
|  None of the Above (select waiver below) |

3. * Select all electronic signature platforms that apply to this consent / assent group:

- Not using electronic signature platforms**
- DocuSign Part 11 (FDA regulated studies)
- DocuSign (standard platform for non-FDA regulated studies)
- REDCap e-Consent
- iMedConsent (Veterans Affairs studies)
- Other electronic signature platform

4. If Other is selected, explain:

5. * Select any waivers that apply to this consent / assent group:

- | |
|---|
|  No Waivers Requested |
|  Waiver of All Consent or Some Elements in Consent Form |
|  Waiver of Parental Permission or Legally Authorized Representative Consent |
|  Waiver of All Assent by Child or Decisionally Impaired Adult |

Waiver of Signature on Consent/Permission Forms (waiver of documentation of consent)

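### The plan conflicts on whether survey completion is tracked per respondent and shows no count of surveys offered or declined, so the response rate for the LAR and provider surveys is not assured

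*Combined protocol and SAP*

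**What the plan says.** Acceptability is part of Aim 1. It is measured by voluntary electronic surveys when a patient's participation ends (Study Procedures, Q6). The plan describes how completion is tracked in three places.

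- **Waiver of Some or All Elements of Consent, Q4 and Q6** (LAR and provider surveys): the team "will only maintain a log of number of surveys completed". The rule appears in both answers. Q5 of the same section treats these responses as essential to the study's aims.
- **Populations with Special Considerations, Q2** (employees): "there is no record of whether individual providers completed the survey or not".
- **Active Internet Data Collection, Q2** (Q1 there covers providers, patients and LARs): "the study team will solely be informed of whether or not the survey was completed by each survey contender". The answers themselves are anonymous: "The data will be unlinked to any identifiers (including email addresses, names, and/or IP address or participant numbers".

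A respondent may decline. The Consent Groups entries for providers and LARs let the person "return the iPad to the study team member without completing the survey". The group sizes in Study Population, Q3 are ceilings, for example "100 Nurses (upper limit; two for each patient". Study Procedures, Q6 sets the eligibility rule, "Surveys will only be administered if a patient uses the blanket for at least one night", and also plans comparison statistics between VCUMC and CMH.

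**The concern.** A favorable percentage from a voluntary survey is hard to read without knowing how many people were asked and how many refused. Here non-response is likely by design. The iPad can be handed back. LAR and provider surveys are in person only, although an LAR may have consented by telephone and may never be at the bedside. The staff asked are those assigned on the day.

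If only completed surveys are counted, three different events leave the same trace, which is none: a refusal, a person who was not there, and a person nobody approached. The first bears on acceptability of the blanket. The other two bear on study logistics. A count of offers not made at the time cannot be rebuilt exactly afterwards. Because the pilot is meant to support a larger randomized trial, readers will want to know how far the acceptability figures depend on who answered.

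**Working it through.** **1. The plan's own totals.** Study Population, Q3 gives 50 patients, 50 LARs, 100 nurses and 100 medical providers. 50 + 50 + 100 + 100 = 300, as stated. Adding 125 screening failures and 75 who do not enroll gives 500, as stated. The groups under the count-only rule (LARs, nurses, providers) sum to at most 50 + 100 + 100 = 250.

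**2. The three statements side by side.**

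| Section | Groups covered | What is kept |
|---|---|---|
| Waiver of consent, Q4 and Q6 | LARs, providers | number completed |
| Special populations, Q2 | providers | no record by individual |
| Internet data collection, Q2 | providers, patients, LARs | completed or not, for each intended respondent |

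The first two fit together. The third stands against both, most directly against the second for providers. None of the three mentions surveys offered, declined or returned blank, or people who were unavailable.

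**3. Response rate from a completed count alone.** Let *c* be the number completed and *M* the ceiling. The number offered lies between *c* and *M*, so the response rate lies between *c/M* and *c/c* = 100%. The plan states no expected response, so the values of *c* are assumptions:

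- Nurses, *M* = 100: *c* = 40 gives 40% to 100%; *c* = 60 gives 60% to 100%; *c* = 80 gives 80% to 100%.
- LARs, *M* = 50: *c* = 30 gives 30/50 = 60% to 100%.

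**4. Effect on a favorable share.** Let *a* of the *c* completers be favorable. Over all *M* possible respondents the share lies between *a/M* (every other person unfavorable) and *(a + M − c)/M* (every other person favorable). With *M* = 100 and 80% of completers favorable (assumed):

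| *c* | *a* | lower bound | upper bound |
|---|---|---|---|
| 40 | 32 | 32/100 = 32% | (32 + 60)/100 = 92% |
| 60 | 48 | 48/100 = 48% | (48 + 40)/100 = 88% |
| 80 | 64 | 64/100 = 64% | (64 + 20)/100 = 84% |

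**5. What an offered count would add.** Suppose 18 of 20 completed surveys are favorable, 90%. If 20 were offered, 90% stands. If 40 were offered, the share among those offered lies between 18/40 = 45% and (18 + 20)/40 = 95%. A completed-only log holds the same entry, 20, in both cases.

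**6. How far the denominator can be rebuilt.** Blanket use is recorded: "Hourly rounding by a study champion will be utilized to document blanket use between the hours of 7pm-7am". The number *E* of patients with at least one night of use can therefore be counted. The per-patient ceilings then give at most *E* LARs, 2*E* nurses and 2*E* medical providers. At *E* = 50 these are the 50, 100 and 100 above; a smaller *E* narrows the ranges. They remain ceilings, because Study Procedures, Q6 speaks of the patient's nurse in the singular and of physicians and/or advanced practice providers, so the number due per patient is not fixed.

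**7. By site.** With 25 patients per site the ceilings are 25 LARs, 2 × 25 = 50 nurses and 50 medical providers at each. If 30 nurse surveys were completed at each site (assumed), the response could be 30/50 = 60% at one and 100% at the other, and a completed count would not show it.

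**The case against.** The strongest reply is that the internet data collection section already supplies the denominator. Completed-or-not status for each intended respondent gives a response rate, and that section covers all three respondent types. This stands, provided that section prevails over the other two. It would still not separate refusal from absence or from never being approached.

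A second reply is that the word 'only' in the waiver section is a privacy promise, made in answer to questions on risk and identifiability, and was not meant as a data-management rule. Being informed of completion at handover while keeping no named record would also be workable. That is a fair reading, but the text does not say so, and it leaves the offered count unplanned.

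Third, the Data Collection Spreadsheet and survey instruments are listed but not shown. They may contain fields for offers and refusals. This cannot be checked, so the point concerns the visible text only.

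Four stronger readings are tempting, and the documents do not support them:

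- A reader might infer that no response rate can be given for any acceptability result. The waiver section does not cover the patient survey, the internet section may supply completion status, and documented use with the per-patient ceilings gives a lower bound.
- A reader might see three mutually inconsistent positions. There are two.
- A reader might infer that a difference between hospitals could arise simply from approaching more staff at one of them. The number approached does not by itself shift a proportion; selective approach or differential non-response would.
- A reader might assume that decliners think less of the blanket. The documents give no evidence either way, which is why bounds are the right tool.

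**Conclusion.** The point holds in a limited form. The sections conflict on whether completion is tracked per respondent, and no visible text plans a count of surveys offered or declined. If the waiver and employee sections are followed, the LAR and provider response rate is known only as a range from completed over the ceiling to 100%. On the assumed figures, 60 of at most 100 nurse surveys with 80% favorable leave bounds of 48% to 88%. Reasons for non-response, and any difference in non-response between VCUMC and CMH, could not be assessed.

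The size depends on the assumed number completed and on the ceilings being the true maximum. Whether acceptability is among the planned site comparisons is not stated. This is a descriptive pilot and no analysis is invalidated. The change is still worth making, because the lost denominator belongs to data that the plan itself treats as essential.

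**What to change.** Replace the completed-only log with an unnamed tally by site and respondent role (patient, LAR, nurse, physician or advanced practice provider), with columns for due, offered, declined or returned blank, not available, and completed. Define how many nurses and medical providers are due per patient. Keep the answers unlinked, as now. Align Active Internet Data Collection Q2, Waiver of Consent Q4 and Q6, and Populations with Special Considerations Q2 to that one description. Beside each acceptability result, report the response rate by role and site, with best-case and worst-case bounds.

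The cost is a one-page tally sheet and a small amendment to the waiver text. Anonymity is kept, because the tally holds neither names nor answers. In cells with few people, counts should be reported with care.

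Review Setup lists a continuing-review category in which only data analysis remains. If collection has ended, a prospective tally is no longer possible. The report should then state which log was kept and give bounds against the number of survey-eligible patients and the per-patient ceilings.

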****The IRB will expect studies to operationalize all selected checkboxes into the conduct of the research.**

To elaborate on any response, also click the Other Protections checkbox to provide further explanation in the last free-text question.

Read the entire page before filling out the form.

1. * Protections when conducting one-on-one in-person interventions or interactions (for groups see Q2 below):

- Conducting study activities in locations that maximize privacy (limited people around, closing doors, drawing drapes around beds, monitoring voice volume, etc.)**
- Verifying identity before discussing personal information.**
- Asking the participant if they are comfortable answering questions in that location
- Asking the participant if they are comfortable with having other people present (if any)**
- Moving away from other people when conducting activities in public spaces or offering a private space
- Offering other options of ways to respond to sensitive questions (i.e. pointing, clicking, or writing) if uncomfortable verbally responding
- Using generic signs on research rooms and spaces, particularly for research on stigmatizing or sensitive topics
- Other protections not listed in this question describe below
- N/A study has no in-person interventions or interactions with participants

2. * Protections when conducting group interventions or interactions:

- Conducting study activities in locations that maximize privacy (limited people passing by, closing doors, monitoring voice volume, etc.)
- Moving to a more private area to answer questions or to discuss concerns
- Discussing privacy with the participants and the importance of not talking outside the group about what other people say during the group session
- Allowing participants to use a pseudonym or limiting use of individuals names during the group activity
- Asking everyone in a public group setting (e.g. classrooms, workshops) to turn something in (blank or filled) so participants do not have to self-identify when turning in materials
- Collecting paper forms in a closed box or envelope rather than passing to others or leaving in an open area
- Limiting participant identifiers that would be visible on paper documents (i.e. using study IDs instead of direct identifiers)
- Allowing people to distance themselves from other participants during group activities
- Offering other options of ways to respond to sensitive questions (i.e. pointing, clicking, or writing instead of speaking)
- Using generic signs on research rooms and spaces, particularly for research on stigmatizing or sensitive topics
- Ensuring non-participating individuals are not captured on recordings or in photos
- Other protections not listed in this question describe below
- N/A study has no group interventions or interactions**

3. * Protections when conducting remote interventions or interactions (e.g. phone, text, email, video-conference, tele-health, online, etc.):

- Conducting study activities in locations where study staff can maximize their own privacy (limited people around, closing doors, monitoring voice volume, etc.)**

- Leaving/sending generic messages that avoid using study and participant identifiers, such as names, study titles, clinics, study topics, etc.
- Obtaining permission prior to sending text messages
- Advising the participant to move to a location where they are comfortable answering questions and will not be overheard - incorporate this instruction into your study materials
- Advising online participants to complete the activity at a time and location where they will be comfortable answering questions - incorporate this instruction into your study materials
- Ensuring non-participating individuals are not captured on recordings or in photos
- Offering other options of ways to complete the activity (i.e. online, paper, phone) if more privacy is desired
- Offering a way to save and return later to the online activity if privacy is compromised
- Other protections not listed in this question describe below
- N/A study has no remote interventions or interactions with participants

4. * Protections when mailing study materials to/from participants:

- Obtaining permission to mail study materials
- Confirming/verifying the accuracy of addresses before mailing items
- Ensuring the participant is able to personally receive mailed materials and has a way to protect their own privacy if they do not want others to know they are receiving research communications (i.e. notifying participants of when to expect it)
- Using return address labels and document headers that avoid study identifiers, such as study names, clinics, study topics, etc.
- Avoiding or limiting use of participant identifiers and health information on mailed documents (i.e. using study IDs instead of direct identifiers)
- Providing a return mailing address label or pre-addressed envelope to ensure returned items are sent to the correct address
- Communicating receipt of mail from participants and/or asking them to notify you when they mail it to ensure study documents are not lost in transfer
- Offering other options of ways to complete the activity (i.e. by phone or online) if desired
- Other protections not listed in this question describe below
- N/A not mailing any materials to/from participants

5. * Protections when analyzing or disseminating study data *Applicable to all studies*:

- Working only in locations where the study team can ensure privacy (not working in close proximity to non-study personnel, closing doors, closing/putting away documents/files before leaving, etc.)
- Securing physical materials only in locations that ensure privacy (access limited to authorized study personnel)
- Obtaining explicit parental permission before disseminating or sharing recordings or photos of children
- Blurring/redacting/hiding faces and other identifiable features/marks (tattoos, scars, birthmarks, distinctive voice, etc.) in recordings or photos prior to disseminating or sharing
- Only publishing or presenting aggregate results or findings (i.e. no individual-level information)
- Taking additional steps to protect participant identities when publishing or presenting individual-level information, quotations, results, images describe below
- Other protections not listed in this question describe below

6. Describe any other way(s) that the research team will protect participants' privacy. See the help text for additional guidance.

ID: MS12_HM20027241

View: SF2 - Data Confidentiality and Storage

Data Confidentiality and Storage

Confidentiality refers to the way private, identifiable information about a participant or defined community is maintained and shared. It describes how the studys research materials (data, specimens, records, etc.) are protected from unauthorized access.

Instructions for this page:

Select all the ways that the research team will keep the study materials and data confidential throughout the course of the study. Not all will be applicable to every study.

To elaborate on any response, also click the Other Protections checkbox to provide further explanation in the last free-text question.

Read the entire page before filling out the form.

1. * Protections for paper research materials:

- Maintaining control of paper documents at all times, including when at an off-campus location
- Limiting or avoiding use of participant identifiers on paper documents (i.e. using study IDs instead of direct identifiers)
- Storing paper documents in a secure location accessible only to authorized study personnel
- Promptly transcribing, scanning, or abstracting data from paper into electronic platforms with destruction of the paper copy
- Proper destruction of paper records (and obtaining prior permission when required) in accordance with VCU Records Management policies
- Other protection not listed in this question describe below

N/A no paper research materials

2. * **Protections for research specimens:**

- Maintaining control of specimens at all times, including when at an off-campus location
- Storing specimens in a secure location accessible only to authorized study personnel
- Labeling specimens with subject ID or other coded information instead of direct identifiers
- Final destruction of specimens will be in accordance with VCU policies and specimen containers will be devoid of any identifiable information
- Other protection not listed in this question describe below
- N/A no research specimens**

3. * **Protections for electronic files/data - See <https://ts.vcu.edu/about-us/information-security/data-management-system/>**

- *Required for all studies* Use VCU-approved methods of data storage, transmission, and transfer (see <https://dms.vcu.edu>)**
- Remotely accessing VCU network storage to store data when at off-campus locations
- Ensuring unauthorized individuals who might share a device do not have access to study materials (e.g. individual logins, separate accounts)**
- Using VCU-approved data collection tools and apps (e.g. REDCap) and storing exported analysis files in VCU-approved storage locations (see <https://dms.vcu.edu>)**
When using non-VCU-approved electronic data collection tools, storage locations, data transfer platforms, and mobile apps (e.g. Dropbox, Box, Survey Monkey, Fitbits, novel apps, multi-site data collection platforms): consulting with VCU Information Security on proper data management (see <https://ts.vcu.edu/askit/essential-computing/information-security/>);
advising participants about the terms of use and privacy policies of those sites/apps;
limiting or avoiding use of identifiers; and
removing data promptly from the external location after transferring it to a VCU storage location
- Other protection not listed in this question describe below
- De-identifying the research data by replacing subjects names with assigned subject IDs**
- Storing the studys linkage key in a password-protected and VCU-approved storage location (see <https://dms.vcu.edu>)**
- When analyzing particularly sensitive information, using computers that are unconnected from the internet.
- Proper destruction of electronic records (and obtaining prior permission when required) in accordance with VCU Records Management policies**
- Other protection not listed in this question describe below

4. * **Protections for computers and research devices/apps that are provided to participants for use in the study and taken out of the lab (i.e., giving participants a phone or iPad to take home, wearable trackers, apps, etc.):**

- Transferring data promptly from the device/app given to the participant to a VCU storage location
- Setting strong passwords on computers and research devices (when applicable) that leave VCU with participants
- Device/app set up by VCU Information Security
- When providing devices or mobile apps to children, informing parents about the settings and how to manage them (if applicable), internet access, and any other installed apps on the device
- Other protection not listed in this question describe the device/app and protection below
- N/A no computers or devices/apps being provided for participant use outside the lab**

5. * **Protections for email/online communications**

- Only using VCU/VCU Health email addresses for study-related communications
- Only using VCU/VCU Healthapproved methods of teleconferencing or video conferencing (e.g. Zoom) (for studies involving HIPAA, contact VCU or VCU Health Information Security [as appropriate] about HIPAA-compliant systems)**
- Other protection not listed in this question describe below
- N/A no email/online communications

6. **Specify any other places where this studys paper and electronic research data and/or physical specimens will be stored and any other ways they will be secured from improper use and disclosure.**

See the help text for additional guidance.

Not applicable

7. * **If research data/specimens will be sent/released to person(s) or group(s) outside of the VCU study team or the PIs department for the conduct of this protocol (not for future sharing),**

1) identify the data/specimen recipient(s) along with their VCU department or other institutional or organizational affiliation(s).

2) give a description of what identifiers and/or codes will accompany the data/specimens.

If data/specimens are not being sent/released outside of the VCU study team or the PIs department, state that:

Not applicable - will not be sent/released outside of the VCU study team.

8. * **Select all identifiers that will be collected at any time as part of this study (including for recruitment, data gathering, data analysis, etc.), even if the data will eventually be anonymized:**

- Names**
- Geographic Locators Below State Level**
- Social Security Numbers
- Dates (year alone is not an identifier)**
- Ages over 89 (age under 89 is not an identifier)**
- Phone Numbers
- Facsimile Numbers
- E-mail Addresses

Medical Record Numbers

- Device Identifiers
- Biometric Identifiers
- Web URLs
- IP Addresses
- Account Numbers
- Health Plan Numbers
- Full Face Photos or Comparable Images
- License/Certification Numbers
- Vehicle ID Numbers
- Other Unique Identifier
- No Identifiers
- Employee V#

9. * If the study will code (i.e. de-identify) the research data by replacing subjects names and/or other identifiers with assigned subject IDs, explain the following aspects of the coding process:

- The process for how subject IDs will be generated/assigned (e.g. random, sequential)
- Whether there will be a key that links the subject ID with direct identifiers. If there will be no linkage key, state that.

If a key will be created, describe

- The place where the key will be stored
- The role(s) of all individuals who will have access to the key
- When the key will be destroyed

See the help text for guidance.

Subject IDs for patient participants will be generated sequentially at each site. There will be a key that will be kept in the locked office of the study coordinator that links the participants name with a study ID. Only study personnel will have access to this key. The key will be destroyed at the end of the study, once the study is closed with the IRB.

ID: MS12_HM20027241

View: SF2 - Data Retention

Data Retention

1. * Select all of the ways that individually identifiable information obtained during pre-screening and/or screening will be handled for individuals who **DO NOT** qualify for the study:

- N/A - study does not require screening procedures
- Immediately destroy the information and identifiers (no data collected)
- Immediately destroy the identifiers connected with the data (anonymization)**
- Store until the end of study & then destroy
